5.1.7 Follow-Up (Visits 4 to 11)

Following discharge from the hospital after transplantation, follow-up visits will be performed to determine whether the genetically modified cells have engrafted and are able to produce mature lymphoid and hematopoietic cells containing and expressing the *ADA gene*, and the extent and time-course of immune reconstitution.

The subjects will be evaluated at the following time-points: Month 1, 3, 6, 9, 12, 18, and 24 (end of study visit). Because of the large number of blood tests planned and the limited volumes of blood that can be obtained from young children, it may not be possible to perform every scheduled investigation listed below at each time-point. Therefore, the priority for the ranking of blood tests will be as per the order presented for each visit. The following examinations will be performed:

Month 1/Day 30 (Visit 4 - +/- 1 week)

- Physical examination, vital signs, height, weight and interval history (including routine review of systems, including infectious symptoms (e.g., fever), AEs and concomitant medications),
- Use of PEG-ADA and IgG replacement therapy will be documented. Please note PEG-ADA administration will be stopped at this visit,
- Hematology and biochemistry panels,
- Monitoring for severe infections and/or opportunistic infectious episodes at each study visit,
- Immune function testing;
 - o Determination of absolute numbers of CD3+, CD4+ and CD8+ T-lymphocytes, CD19+ B-lymphocytes and CD56/CD16+ (or CD56+/CD3-) NK cells, CD4+/CD45RA+ (naïve) and CD4+/CD45RO+ (memory) T cells,
 - o Serum immunoglobulin (IgG, IgA, IgM).
- Gene transduction/expression;
 - o Measurement of ADA expression in erythrocytes by ADA enzymatic assay and deoxyadenine nucleotides in RBC.

Day 42 (Visit 5 - +/- 1 week)

The Day 42 assessment will use laboratory parameters to confirm if hematologic reconstitution has occurred. A failure of hematologic reconstitution is defined as persistent ANC < 200/ μ l or platelets < 20,000/ μ l on three independent and consecutive determinations over at least ten days after day 42 from the day of cell infusion. If hematologic reconstitution has not taken place by Day 42 the backup HSC sample will be processed according to the instructions in [Section 3.7](#)

PROTOCOL AMENDMENT 4: VERSION 5.0, 28 MARCH 2018

PAGE 54/130

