- Assessment of re-initiation of PEG-ADA therapy and use of IgG replacement therapy will be documented. Please note: subjects should have discontinued PEG-ADA treatment at Visit 4 (Month 1/Day 30),
- Hematology and biochemistry panels,
- Monitoring for severe infections and/or opportunistic infectious episodes at each study visit,
- Immune function testing;
 - Determination of absolute numbers of CD3+, CD4+ and CD8+ T-lymphocytes, CD19+ B-lymphocytes and CD56/CD16+ (or CD56+/CD3-) NK cells, CD4+/CD45RA+ (naïve) and CD4+/CD45RO+ (memory) T cells;
 - T-cell proliferative responses to PHA,
 - Serum immunoglobulin (IgG, IgA, IgM),
- Gene transduction/expression;
 - Measurement of ADA expression in erythrocytes by ADA enzymatic assay and deoxyadenine nucleotides in RBC.

Month 12 (Visit 9 - +/- 4 weeks)

- Physical examination, vital signs, height, weight and interval history (including routine review of systems, including infectious symptoms (e.g., fever), AEs and concomitant medications),
- Evaluation of quality of life using the Karnofsky/Lansky scale and questions relevant to general well-being, school attendance, and ability to practice sports, respectively,
- Assessment of re-initiation of PEG-ADA therapy and use of IgG replacement therapy will be documented. Please note: subjects should have discontinued PEG-ADA treatment at Visit 4 (Month 1/Day 30),
- Hematology and biochemistry panels,
- RCL assay in PBMC,

- Serum to be banked for possible Western blot testing for RCL (testing performed if the RCL assay in PBMC returns a positive result),
- Vector integration analysis,
- Monitoring for leukemia (by nrLAM-PR) if the criteria for triggering nrLAM-PCR are fulfilled. A blood sample will be taken unless clinical/hematologic findings indicate potential leukoproliferation, whereby a bone marrow sample will be required,
- Monitoring for severe infections and/or opportunistic infectious episodes at each study visit,
- Immune function testing:
 - o Determination of absolute numbers of CD3+, CD4+ and CD8+ T-lymphocytes, CD19+ B-lymphocytes and CD56/CD16+ (or CD56+/CD3-) NK cells, CD4+/CD45RA+ (naïve) and CD4+/CD45RO+ (memory) T cells;
 - o T-cell proliferative responses to PHA,
 - o Measurement of serum immunoglobulin levels (IgG, IgA, IgM) if not receiving immunoglobulins,
 - o Measurement of specific antibodies to tetanus toxoid only if subjects have stopped immunoglobulin replacement and have received tetanus vaccination,
 - o TREC,
 - o TCR V β usage,

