| Visit window | +/- 1 week | +/- 1 week | +/- 2 weeks | +/- 2 weeks | +/- 2 weeks | +/- 4 weeks | +/- 4 weeks | +/- 4 weeks | |
| Physical examination | X | | X | X | X | X | X | X | X |
| Vital Signs | X | | X | X | X | X | X | X | X |
| Weight (kg) | X | | X | X | X | X | X | X | X |
| Height (cm) | X | | X | X | X | X | X | X | X |
| Biochemistry sample ² | X | X | X | X | X | X | X | X | X |
| Hematology sample ³ | X | X | X | X | X | X | X | X | X |
| Questionnaire/QoL scale | | | | X | | X | X | X | X |
| Infectious episodes | X | | X | X | X | X | X | X | X |
| Adverse events | X | X | X | X | X | X | X | X | X |
| Concomitant Medication ⁴ | X | X | X | X | X | X | X | X | X |
| Record IgG and PEG-ADA therapy received | X | X | X | X | X | X | X | X | X |
| Immune function ^{5,6} | X | | X | X | X | X | X | X | X |
| Serum banking for RCL | | | X | X | | X | | X | X |
| Vector integration analysis | | | X | X | | X | X | | |
| Leukaemia assessment ⁷ | | | | X | | X | X | X | X |
| T-cell proliferation to PHA | | | | X | X | X | X | X | X |
| Antibodies to tetanus toxoid | | | | | | X | X | X | X |
| Presence of ADA gene in PBMC/granulocytes and/or lineage-sorted cells | | | X | X | | X | | X | X |
| RCL assay in PBMC | | | X | X | | X | | X | X |
| ADA enzymatic assay | X | | X | X | X | X | X | X | X |
| Deoxyadenine nucleotides in RBC | X | | X | X | X | X | X | X | X |
| Responder assessment ⁸ | | | | X | | | | | |

1. Day 42 assessment will use laboratory parameters to confirm if hematologic reconstitution has occurred. If this has not happened by Day 42 rescue medication, as per standard institute procedure, will be implemented. Any treatment administered to the subject will be recorded in the eCRF.
 2. Biochemistry samples will include the assessment of parameters listed in Table 3. Albumin ALT, AST, ALP will be measured at all time points indicated in this table. Total bilirubin, total protein, total protein, creatinine, blood urea, sodium, potassium, chloride, and calcium will be measured at screening, baseline, Day 1 and all follow-up visits (Month 1 to Month 24). Magnesium and phosphate will be measured only at baseline and the conditioning time points.
 3. Hematology samples will include the assessment of parameters listed in Table 3 and will be measured at all time points indicated in this table.
 4. Standard post-transplant medication will be administered from Day 0 and recorded in the eCRF.

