5. Immune function will be assessed by absolute numbers of CD3+, CD4+ and CD8+ T-lymphocytes, CD19+ B-lymphocytes and CD56+/CD16+ (or CD56+/CD3-) NK cells, CD4+/CD45RA+ (naïve) and CD4+/CD45RO+ (memory) T cells, TREC levels, TCR V β usage, lymphocyte response to PHA (if sufficient cells), and serum immunoglobulin (IgG, IgA, IgM).
6. If IgG treatment is stopped, immunoglobulin levels will be required every month for the first 3 month after discontinuation. This is to ensure IgG levels hold before commencing vaccinations as per standard institute protocols.
7. A blood sample will be taken unless clinical/hematologic findings indicate potential leukoproliferation, whereby a bone marrow sample will be required. In addition to the time points specified in this table, this assessment should be performed if the nrLAM-PCR criteria is fulfilled (see Section **Error! Reference source not found.**).
8. Responder assessment includes: erythrocyte ADA enzyme activity, immune reconstitution, and gene-marked granulocytes as described in Section **Error! Reference source not found.**

Abbreviations: ADA=adenosine deaminase, ALP=alkaline phosphatase, ALT=alanine aminotransferase, AST=aspartate aminotransferase, eCRF=electronic case report form, ET=early termination, IgA=immunoglobulin A, IgG=immunoglobulin G, IgM=immunoglobulin M, N/A=not applicable, NK=natural killer, PBMC=peripheral blood mononuclear cells, PCR=polymerase chain reaction, PEG= polyethylene-glycol, PHA= Phytohemagglutinin, QoL=quality of life, RBC=red blood cell, RCL= Replication Competent Lentivirus, TCR= T-cell receptor, TREC= T-cell receptor excision circle.

4 Study Objectives

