5.3 Exploratory Endpoints

Exploratory endpoints for this study are laboratory correlates of efficacy that will be used to assess the level of gene correction, engraftment and immune reconstitution.

6 Timing of Analyses

The statistical analyses of efficacy data from this study will be performed in three stages:

- The first analysis will be carried out when a minimum of 5 subjects have completed 6-months follow-up post OTL-101 infusion. At this analysis, the success/failure of the OTL-101 cryopreserved infusion will be defined by the three criteria listed in the primary

objectives. This data will be compared with available data from UCLA ongoing Phase I/II study, treated with the OTL-101 fresh formulation. This will support the CMC comparability data between OTL-101 cryopreserved and fresh formulations. Secondary and exploratory endpoints will also be described and compared with the data from the fresh study.

- The second analysis will be carried out when all subjects have completed 12-months follow-up post GTMP administration. At this analysis, overall survival and event free survival will be evaluated. Secondary and exploratory endpoints, as well as baseline characteristics, subject disposition, and safety data will also be described.
- The third and final analysis will be performed to determine the overall survival and event free survival for all subjects 24 months post GTMP administration. Secondary and exploratory endpoints, as well as baseline characteristics, subject disposition, safety and busulfan pharmacokinetic (PK) data will also be described.

7 Analysis Populations

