8.3 Efficacy Evaluations

8.3.1 Primary Efficacy Endpoints

8.3.1.1 Response to OTL-101 Treatment at 6 Months

Response to OTL-101 treatment at 6 months post administration will be based on the following criteria:

- ADA activity in red blood cells: change from baseline >0 Units,
- Absolute CD3+ T-cell count $\geq 200/\text{mm}^3$, and
- Detectable gene-marked granulocytes by differential polymerase chain reaction (dPCR)/qPCR $\geq 1/10,000$ cells.

Subjects who meet all three criteria will be said to have mounted a response.

For any subjects with missing values at 6 months, the earliest assessments after month 6 will be used. In addition, if ADA activity at baseline is not available, any positive value will be considered as a positive response.

The number (%) of subjects mounting a response will be summarized and descriptively compared with the proportion from the UCLA “Fresh” study. In addition, the number (%) of subjects with a response to each of the individual criteria will be summarized.

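### A missing Month 6 response component is replaced by the next later value with no time limit, so a 6-month response can rest on Month 9, Month 12 or later data

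*SAP*

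**What the plan says.** SAP 8.3.1.1 defines response at 6 months by red-cell ADA activity, CD3+ count and gene-marked granulocytes: "Subjects who meet all three criteria will be said to have mounted a response". For missing data it says: "For any subjects with missing values at 6 months, the earliest assessments after month 6 will be used". The section gives no latest acceptable date, no rule for a subject with no later value, no restriction on values taken after PEG-ADA restart or rescue HSCT, and no sensitivity analysis. Protocol 9.3.1 and 9.6.4, which define and analyse the same endpoint, have no missing-data rule.

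In SAP Table 2 the row "Presence of ADA gene in PBMC/granulocytes and/or lineage-sorted cells" is marked at Months 3, 6, 12 and 24 and at early termination, but not at Month 9 or 18. ADA activity and immune function (which includes CD3+) are marked at Months 6, 9, 12, 18 and 24 and at early termination.

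On timing, SAP section 6 says: "The first analysis will be carried out when a minimum of 5 subjects have completed 6-months follow-up post OTL-101 infusion". Protocol 5.1.7 warns that, because of blood volume in young children, "it may not be possible to perform every scheduled investigation listed below at each time-point". Protocol 6.2.1.1 keeps subjects who restart PEG-ADA in follow-up. SAP 7.1 puts every treated subject in the efficacy population.

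**The concern.** The Month 6 visit has a ±2 week window, but the replacement rule has none. A component missed at Month 6 can be filled by a measurement made months later, and the subject is still reported as a 6-month responder. Three things are at stake.

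- **What is estimated.** The rate is compared, descriptively, with the UCLA fresh-formulation study to support comparability. A rate mixing Month 6 with Month 9–12 or later values is not a clean 6-month rate, and the SAP does not say that the fresh data follow the same rule.
- **Attribution.** A later value may be taken on restarted PEG-ADA. Protocol 1.1.2.1 itself credits enzyme replacement with metabolic correction and some, often incomplete, immune reconstitution.
- **Stability.** At the first analysis a Month 9 or Month 12 replacement may not yet exist. A subject's status could be undetermined then and become a response later.

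**Working it through.** **Inputs.** Replacement rule and response definition: SAP 8.3.1.1. Schedules and windows: SAP Table 2 and Protocol 5.1.7. N = 10 and the precision statement: Protocol 9.4. First analysis with at least 5 subjects: SAP section 6.

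**1. How late a replacement can be.** One month is taken as 30.4375 days.

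| Component | Next scheduled visit after Month 6 | Nominal delay | Latest in-window date |
|---|---|---|---|
| ADA activity, CD3+ | Month 9 ±2 weeks | 9 − 6 = 3 months | 9 + 14/30.4375 = 9.5 months |
| Gene marking | Month 12 ±4 weeks | 12 − 6 = 6 months | 12 + 28/30.4375 = 12.9 months |
| Gene marking, Month 12 also missing | Month 24 ±4 weeks | 24 − 6 = 18 months | 24 + 28/30.4375 = 24.9 months |

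The Month 6 window closes at 6 + 14/30.4375 = 6.5 months. An early termination visit, if one occurs, could supply a value sooner.

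**2. The plan's own precision figure.** Protocol 9.4 states 15% as the half-width of the two-sided exact 95% interval at 100% success with N = 10. For n/n the exact lower limit is 0.025^(1/n). For 10/10 this is 0.025^(1/10) = 0.6915, and the half-width is (1 − 0.6915)/2 = 15.4%. The stated figure is reproduced.

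**3. Direction.** Under missing = not met, a subject with a missing component is a non-responder. Under replacement, that subject either stays a non-responder or becomes a responder. Relative to that benchmark the rate can therefore stay the same or rise, but cannot fall. The rule changes nothing for a subject with an observed Month 6 failure, because one failed component already makes a non-responder.

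**4. Size for one subject.** Assume all others respond. For x responders of n, the exact limits are the 2.5% quantile of Beta(x, n − x + 1) and the 97.5% quantile of Beta(x + 1, n − x).

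| Handling of the one subject | N = 10 | n = 5 |
|---|---|---|
| Missing = not met | 9/10 = 90% (55.5–99.7) | 4/5 = 80% (28.4–99.5) |
| Replaced by a later value that passes | 10/10 = 100% (69.2–100) | 5/5 = 100% (47.8–100) |
| Difference | 10 points | 20 points |

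**5. How often the rule might be used.** The documents give no missingness rate. If each subject independently has chance d of lacking a Month 6 gene-marking value (an assumption), the chance of at least one among n is 1 − (1 − d)^n. For d = 5%, 10% and 20% this is 40%, 65% and 89% with n = 10, and 23%, 41% and 67% with n = 5. These are chances that the rule is invoked, not that it changes the result wrongly.

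**The case against.** The strongest defence is that a later value is a fair stand-in. Protocol 9.4 says the three parameters plateau between 3 and 4 months. Protocol 2.1 describes granulocyte marking as stable up to 2 years and red-cell ADA as stable up to 24 months. If that holds here, replacement introduces little error, and scoring a sample missed for blood volume as a failure would bias the rate downward. This stands as a reason not to assume a large bias. It does not settle the matter: the ADA and gene-marking experience in Protocol 2.1 comes from the fresh product, and Protocol 1.4.2.1 allows that the cryopreserved product may not work as well.

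Other points also stand:

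- A reader might infer that the rule can only inflate the rate because Month 6 failures are withdrawn. The documents do not support that. Observed failures are non-responders already, and a replacement below threshold scores a non-responder. If the alternative were to exclude the subject, the rule could lower the rate: 9/10 instead of 9/9.
- A reader might infer that only subjects still in the study can supply a later value. The early termination visit (Protocol 5.1.8) includes all three assays.
- A reader might infer that the primary assays are first to be dropped when blood is short, because gene transduction and expression come last in the Month 6 list. But the responder assessment is also listed there, ahead of every other blood test, so the ranking is at worst ambiguous.
- The response definition does not exclude subjects on restarted PEG-ADA at Month 6 either, and event-free survival counts the restart as an event. Protocol 6.2.1.1 directs withdrawal of subjects who may go on to allogeneic transplant, so replacement values after HSCT should be rare.
- With all treated subjects in the population and all three criteria required, a subject with no value at all is most naturally read as a non-responder. Stating this is a clarification.
- SAP 8.3.1.1 plans counts and percentages with a descriptive comparison. The intervals above are a yardstick, and no type I error is involved.

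**Conclusion.** The concern holds as a defect of specification in a primary endpoint. Followed as written, the rule lets a 6-month response rest on data 3 to 6 or more months late, possibly obtained after PEG-ADA restart, and lets a subject's status change between the first and later analyses. Relative to missing = not met, it can only raise the rate, by 10 points per affected subject at N = 10 and 20 points at n = 5, if the others respond and the later value passes.

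A reader might conclude that the responder rate is biased upward. The documents make that possible but do not show it. The direction depends on the benchmark chosen, the amount of missing data is not stated, and the sponsor's plateau expectation, if it carries over to the cryopreserved product, would make the effect small. The case for change is that the rule is open-ended and cheap to bound, not that harm has been demonstrated.

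**What to change.** In SAP 8.3.1.1:

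- Allow replacement only within a stated window around Month 6 that ends before the Month 9 visit. That visit's window opens at 9 − 14/30.4375 = 8.5 months. This avoids failing a subject whose sample was drawn just outside ±2 weeks.
- Do not use values taken after PEG-ADA restart or rescue HSCT as replacements.
- Otherwise score the component as not met. Keep all treated subjects in the denominator, and state that deaths and withdrawals before Month 6 are included.
- Report the present open-ended replacement as a labelled sensitivity analysis.
- Apply the same rule to the fresh-study data where those data allow. They are not visible in these documents.

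The cost is SAP wording and one table. The downside is that a sample missed for blood volume and not repeated within the window counts as non-response, so the primary rate may be slightly less favourable. The sensitivity table shows by how much.
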